The treatment alternatives for clinically localized prostate cancer provide similar local control and survival (46). Quality of life (QOL) outcomes are thus an important factor in selecting treatment (47). Several studies have demonstrated that radiation treatment for prostate cancer can adversely affect urinary, bowel and sexual function (25, 26). The severity and duration of these toxicities varies among patients. The expanded prostate cancer index composite (EPIC) has been developed as a disease specific, patient-administered instrument to measure quality of life in men with prostate cancer (48). Thus, acceptance of a novel regimen for treatment of unfavorable-risk prostate cancer patients must not only be effective and have minimal impact on short- and long-term quality of life, but it must also be cost effective (30,49). Quality-Adjusted Life Years (QALYs) are well-established for measurement of cost-effectiveness for many different types of diseases, and can be calculated through use of clinical quality of life measurements, such as the EuroQol EQ-5D (50). These tools will be utilized for longitudinal QOL assessments for the duration this study.

The Philadelphia CyberKnife Experience

The Philadelphia CyberKnife center is a highly specialized radiation oncology facility within the Crozer Keystone Health System with a sole focus on stereotactic radiation therapy services and delivery. As one of the early adopters and pioneers of SBRT techniques, our expertise and experience is on par with nationally renowned academic centers and our physicians serve on national committees and lead multi-institution prospective trials. Our published experience with CyberKnife prostate SBRT has shown favorable biochemical control compared to IMRT cohorts with low toxicity rates (51, 52). We have also compared prostate SBRT to IMRT using a large national database showing no detriment to SBRT compared to IMRT (53, 54). We will leverage our experience, expertise and national standing to conduct this pivotal prospective study.

Updated Clinical Experience for SBRT

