3.0 PRETREATMENT EVALUATION

Evaluations Required for Eligibility:

1. Complete history & physical examination
2. Assessment of performance status
3. Serum PSA (<90 days prior to registration)
4. Pathologic confirmation of adenocarcinoma of the prostate
5. Bone scan (PSMA PET can be substituted for bone scan)
6. Ultrasound of prostate, MRI or CT of pelvis
7. Endorectal/Multi parametric MRI
8. Patient questionnaires (see appendix VI).
 - 1 Expanded Prostate Cancer Index Composite (EPIC)-26 questionnaire
 - EuroQol EQ-5D-5L

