6.0 PATIENT ASSESSMENTS

| Assessment | Pre-entry | | | | Follow-up interval: months post therapy | | | | |
|----------------------------|-----------|---|---|---|---|----|----|-------|---|
| | | 1 | 3 | 6 | 12 | 18 | 24 | 36-60 | |
| History (SHIM, AUA) | X | | X | X | X | X | X | | X |
| Physical exam (DRE) | X | | | X | X | X | X | | X |
| ECOG Performance Scale | X | | | X | X | X | X | | X |
| Prostate Biopsy | X | | | | | | | | |
| PSA | X | | | X | X | X | X | | X |
| Prostate volume assessment | X | | | | | | | | |
| Bone scan | X | | | | | | | | |
| Pelvic imaging | X | | | | | | | | |
| Toxicity evaluation (AUA) | X | | X | X | X | X | X | | X |
| EPIC-26 Questionnaire | X | | | | X | X | | X | X |
| EuroQol EQ-5D-5L | X | | | | X | X | | X | X |

Assessment schedule: Quality of life measurements will take place per the table, then annually through 5 years post-treatment.

7.0 CLINICAL ENDPOINTS:

Patients will have toxicity evaluation weekly during treatment. At 1 month following treatment, patients will be assessed for acute toxicity. At 6, 12, 18, and 24 month intervals (and every year thereafter, through year 5- 10, if investigators opt to continue past year 5), patients will be seen and evaluated, including a history, physical exam, performance status, PSA, toxicity evaluation. In addition, at 6 months, 12 months and annually thereafter, EPIC-26 will be administered. Examination and studies may be done at outside facility. Prostate biopsy, bone scan (PSMA PET/CT may be substituted for bone scan) and pelvic MRI will be performed at time of biochemical or clinical failure.

Criteria for toxicity:

Acute side effects (<=90 days of treatment start) and late side effects (> 90 days of treatment start) will be assessed using the NCI Common Toxicity Criteria version 4.0 (see appendix V).

Criteria for disease control:

1. Biochemical disease free survival (bDFS):
 - a. Phoenix definition (55): failure occurs when the PSA is ≥ 2 ng/ml more than the lowest PSA measurement before the current one, with no backdating. Administration of salvage therapy will be considered failure.

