The target sample size is 100 patients for this Phase II study. Allowing for a 15% ineligibility rate, the total sample size is 115 patients. Accrual is anticipated to be completed within 5 years of institutional IRB approval. This Phase II trial will provide information to guide future Phase III studies. Sample size determination is based on the late toxicity endpoint. A single-stage Fleming design will be used to test the null hypothesis that the late unacceptable radiation toxicity probability at 2 years p is < 0.05 versus the alternative hypothesis that toxicity probability at 2 years is > 0.15 . Unacceptable toxicity will be defined as grade 3 or higher toxicity. If 10 or fewer patients experience late radiation toxicities at 2 years, the null hypothesis will not be rejected and then the regimen will be considered for a phase III study. If at least 10 patients experience late radiation toxicities at 2 years, the null hypothesis will be rejected. This design has a power of 89% and a type I error rate of 0.10.

Analysis Plan

1. Number and percentage of subjects for each toxicity will be summarized overall by body system and by onset time (acute: ≤ 90 days of treatment start and late: >90 days of treatment start). The tabulation will also be separated by toxicities of Grade 3 and above.
Future studies incorporating DE-SBRT would be worthwhile if the rate of grade 3 GU/GI toxicity was $\leq 10\%$.
2. Biochemical disease-free survival, disease-free survival, disease-specific and overall survival curves will be calculated and presented by the methods of Kaplan and Meier.
3. The proportion of patients with local and distant failure will be reported with a 95% binomial confidence interval.
4. General health related and disease specific quality of life measurements will be summarized over time. Graphical displays will be created for each patient's trajectory over time and also summarized using the average for all patients.

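### The group quality-of-life summary is an average not tied to the pre-entry scores, so it can mask a decline if men with poorer scores stop answering

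*Protocol*

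**What the plan says.** Quality of life is a secondary objective (Protocol, section 2.0) and the last of the secondary endpoints (section 8). The introduction says that a new regimen must, among other things, "have minimal impact on short- and long-term quality of life".

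Both questionnaires are required before treatment (section 3.0), and the assessment table marks them at pre-entry (section 6.0). On follow-up, section 6.0 states: "Quality of life measurements will take place per the table, then annually through 5 years post-treatment". Section 7.0 adds that "at 6 months, 12 months and annually thereafter, EPIC-26 will be administered".

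The analysis is item 4 of the Analysis Plan in section 8. Its first sentence is: "General health related and disease specific quality of life measurements will be summarized over time". Its second plans a plot of each man's course, "also summarized using the average for all patients". The item names no change from baseline, no model and no interval. Item 3, just above it, does specify a 95% interval for local and distant failure. No expected rate of questionnaire non-response is given; the 15% allowance in section 8 is for ineligibility.

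**The concern.** Impact on quality of life is a within-man question: how far has he moved from where he started? The trial collects what is needed to answer it, but the only group-level summary in item 4 is an average over time, with no stated link to the starting scores.

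Over 5 years some men will miss questionnaires. If the average at each visit is formed from the scores on hand, the men behind it change from visit to visit. When those with poorer earlier scores are likelier to stop answering, the later average is pulled up although nobody has improved, and comparing it with the pre-entry average shows too small a decline. The trial is meant to inform later phase III work, so an understated effect on quality of life could be carried forward.

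**Working it through.** The protocol states no quality-of-life effect, SD, correlation or attrition, so there is no figure to reproduce. The check shows how large the distortion could be. **Every input below is an assumption.**

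**Inputs.** Score SD 20 at both times; true mean decline 6 points; correlation ρ between baseline and follow-up 0.4 to 0.8; 10% or 30% missing at follow-up. Drop-out depends on the standardised baseline score z: P(missing) = 1/(1 + exp(−(a − s·z))), with s = 0.5 or 1.0 and a set to give the chosen missing rate.

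**Formulas.** Let δ be the mean of z among men who still answer.
- Raw averages (responders' follow-up mean minus everyone's baseline mean): −6 + ρ × 20 × δ.
- Simple paired change among responders: −6 − (1 − ρ) × 20 × δ.
- Baseline-adjusted estimate (regression on baseline, evaluated at everyone's baseline mean): −6, because drop-out here depends only on an observed score.

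Numerical integration gives δ = 0.143 (s = 0.5) and 0.253 (s = 1.0) at 30% missing, and 0.049 and 0.091 at 10% missing.

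**Raw averages, drop-out driven by baseline (truth −6.0):**

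| Missing | s | ρ = 0.4 | ρ = 0.6 | ρ = 0.8 |
|---|---|---|---|---|
| 30% | 0.5 | −4.9 | −4.3 | −3.7 |
| 30% | 1.0 | −4.0 | −3.0 | −2.0 |
| 10% | 0.5 | −5.6 | −5.4 | −5.2 |
| 10% | 1.0 | −5.3 | −4.9 | −4.5 |

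Example: 30% missing, s = 1.0, ρ = 0.6 gives −6 + 0.6 × 20 × 0.253 = −3.0. At 30% missing the apparent decline runs from about 4.9 to 2.0 (a simulation put the upper end at 4.8). At 10% missing the largest bias is 0.8 × 20 × 0.091 = 1.5 points.

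**Other drop-out mechanisms, 30% missing, ρ = 0.6 (s = 0.5 / 1.0, truth −6.0):**

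| Drop-out driven by | Raw averages | Simple paired change | Baseline-adjusted |
|---|---|---|---|
| Baseline score | −4.3 / −3.0 | −7.1 / −8.0 | −6.0 / −6.0 |
| Unseen follow-up score | −3.1 / −0.9 | −4.9 / −4.0 | −4.1 / −2.6 |
| Size of the decline | −4.7 / −3.7 | −3.4 / −1.5 | −4.0 / −2.3 |

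With random drop-out none of the estimates is biased. For 100 men, 70 of them answering, the standard error of the raw difference is 20 × √(1/70 + 1/100 − 2 × 0.6/100) = 2.22; baseline adjustment lowers it to about 2.09.

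**A second set of assumptions** (baseline SD 15, true decline 5, change with SD 12 and independent of baseline, drop-out on baseline at log-odds 1 per SD) gave raw averages of −3.6, −2.4 and −1.2 at 10%, 20% and 30% missing. The direction is the same. Paired change stays at −5.0 there only because change was made independent of baseline; in the main setting, regression to the mean breaks that.

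**The case against.** The strongest reply is that the protocol does not say what a critic might read into it. A reader could infer that item 4 prescribes a raw average of whoever happens to answer. It does not: it speaks of all patients, is silent on missing questionnaires, and its opening sentence leaves the estimator open. The choice of model and the handling of missing forms commonly belong in a statistical analysis plan, which is not at hand, so their absence is not a fault. The same sentence of item 4 also plans individual trajectories, and each can start at the man's own pre-entry score.

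This stands, and it limits the point. What remains is that item 4 is written, and the one group summary it names is not anchored to the baseline the trial collects. An average over all patients cannot be formed literally at a visit that some have missed, so averaging available scores is a plausible reading. Plots for about 100 men show individual courses but give no estimate of average impact.

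A second reply is that baseline anchoring is no cure-all. This is also right. Simple paired change can overshoot (−7.1 to −8.0 against −6.0). If drop-out follows the decline itself, the baseline-adjusted estimate is further from the truth than the raw averages are. The remedy must therefore be specified with care and its limit stated.

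**Conclusion.** The point holds as a conditional one. Item 4 does not tie its group summary to the pre-entry EPIC-26 and EQ-5D-5L scores. If the average is taken over available scores, it can mask a decline when men with poorer earlier scores stop answering. Under the assumed inputs, a true decline of 6 points would appear as about 4.9 to 2.0 at 30% missing; the bias is at most about 1.5 points at 10% missing and nil with random drop-out.

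A reader might go further and infer that the quality-of-life result will be biased towards little impact. The documents do not support that: they give no non-response rate and no sign that non-response will be selective. Nor does it follow that change from baseline removes the problem under every kind of drop-out. This is a cheap improvement to a secondary descriptive endpoint; the sample size and the decision rule rest on late toxicity and do not change.

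**What to change.** Amend Analysis Plan item 4 as follows:
- Keep the individual trajectory plots.
- For each EPIC-26 domain and for EQ-5D-5L, report the mean change from pre-entry at each visit with a 95% CI. Estimate it from a repeated-measures mixed model that uses the baseline and all available follow-up scores, not from a simple paired mean among responders.
- Show completed against expected questionnaires at each visit.

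The cost is analysis wording only, with no new data or visits. The downside is reliance on a missing-at-random assumption, which item 4 should state. The model corrects drop-out explained by observed scores, corrects only partly drop-out driven by the unseen current score, and does not correct drop-out driven by the decline itself. The completion counts let readers judge how much weight that assumption carries.
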